STUDY PROTOCOL

STUDY ON THE SAFETY OF ADMINISTERING ISONIAZID TO SYSTEMIC LUPUS ERYTHEMATOSUS PATIENTS TO PREVENT TUBERCULOSIS

Unique Protocol ID: IPD-202402.01

Document Date: August 1st 2022

NCT Number: N/A

Researcher:

**[name], dr., Sp.PD-KR, M.Kes
(8830960018)**

[name], dr., PhD (0011056602)

**[name], dr., Sp.PD-KPTI, PhD
(8849720016)**

[name], dr., Sp.PD

PADJADJARAN UNIVERSITY

2024

STUDY PROTOCOL

STUDY ON THE SAFETY OF ADMINISTERING ISONIAZID TO SYSTEMIC LUPUS ERYTHEMATOSUS PATIENTS TO PREVENT TUBERCULOSIS

Researcher:

[name], dr., Sp.PD-KR., M.Kes - Division of Rheumatology and Immunology, Department of Internal Medicine, Padjajaran University, Hasan Sadikin Hospital Bandung.

[name], dr, Sp.PD-KPTI, PhD - Division of Tropical and Infectious Diseases, Department of Internal Medicine, Padjajaran University, Hasan Sadikin Hospital Bandung.

[name], dr., PhD - Division of Molecular Biology, Department of Biomedical Sciences, Padjajaran University, Hasan Sadikin Hospital Bandung.

[name], dr., Sp.PD - Department of Internal Medicine, Krida Wacana Christian University.

Aim

This study aims to prove that the administration of Isoniazid (INH) in the prevention of Tuberculosis (TB) in patients with Systemic Lupus Erythematosus (SLE) is safe against liver toxicity and disease recurrence.

Research Design

An open-label, randomized, controlled, prospective cohort study evaluating two groups of SLE patients, those receiving INH and pyridoxine for nine months and those not receiving both drugs. Signs and symptoms of drug-induced hepatotoxicity and degree of SLE disease activity were assessed monthly for the first three months (months 1/2, 1, 2, and 3), and then continued every three months for up to one year (months 6, 9, and 12).

Introduction

Systemic Lupus Erythematosus (SLE) is a highly complex chronic autoimmune disease that affects multiple organs.¹ The course of the disease is influenced by many things, one of which is infection.² SLE patients are more susceptible to infections, due to their disease activity as well as the use of immunosuppressant drugs and glucocorticoids.³ One of the infections that mainly affects SLE patients is Tuberculosis (TB) infection,⁴ especially patients living in Asian areas that are endemic to TB.⁵

TB infection increases the morbidity and mortality of SLE patients, causing more severe disease and death in SLE.⁶⁻¹⁷ The World Health Organization (WHO) has established guidelines for TB prevention in HIV patients.¹⁸ Efforts to prevent TB have been made in HIV patients by administering Isoniazid (INH) prophylaxis and found to significantly reduce the incidence of TB in HIV patients by 35%, with good safety data and no significant increase in drug side effects.¹⁹

[figure not shown]
Prevention of TB in SLE is controversial, and no guidelines have been issued on the subject. An Indian study found an 82% reduction in the incidence of TB in SLE patients with INH prophylaxis.²⁰ However, retrospective studies in Hong Kong and Korea found no significant difference between those given and those not given prophylaxis.^{13,21} No studies have specifically examined the safety of INH prophylaxis in SLE patients. Research is needed on the safety of INH in SLE patients, especially in terms of toxicity to the liver and its effect on disease recurrence, before further research on its effectiveness in preventing TB in SLE patients.

Research Design and Subjects

This is a randomized controlled clinical study involving SLE patients at the Rheumatology Polyclinic, Department of Internal Medicine, Padjadjaran University, Hasan Sadikin General Hospital Bandung,

The diagnosis of SLE is based on the 1997 ACR criteria or 2012 SLICC criteria. The screening included *informed consent*, history taking, physical examination, chest X-ray, and laboratory examination (mainly SGOT/SGPT, HBsAg, anti HCV Total). The examination was conducted to ensure that the subjects did not suffer from active TB, and or impaired liver function. Subjects who meet the inclusion criteria will be randomly divided into two groups, the treatment group receiving INH 5 mg/kg/day (maximum 300 mg/day) and pyridoxine 10 mg/day, and the control group receiving neither drug. Routine SLE medications will be continued throughout the study and recorded at each visit.

The research design is depicted through the chart below:

Inclusion and Exclusion Criteria

Inclusion Criteria

- SLE patients who do not have signs and symptoms of active TB (pulmonary and extrapulmonary),
- SLE patients who are not on TB treatment,
- SLE patients with no history of TB,
- SLE patients who are in remission or low *disease activity state (LLDAS)*, with a history of stable SLE treatment in the last three months and have good liver function,
- Agree to fully participate in this study.

Exclusion Criteria

- SLE patients who have previous liver dysfunction, including hepatitis B or hepatitis C,
- SLE patients who have a history of allergy to INH,
- SLE patients with malignancy,
- SLE patients who are pregnant.

Variables

VARIABLES	DEFINITION	ASSESSMENT	OUTPUTS	DATA TYPE
Systemic Lupus Erythematosus (SLE)	ACR 1997 or SLICC 2012 criteria ^{22,23}	History review, physical examination, laboratory examination	Yes/No	Nominal
Age	Age at the time of study	History review	Year	Numerical
Duration of SLE	Duration from diagnosis of SLE to inclusion in the study.	History review and medical record confirmation	Month	Numerical
Isoniazid (INH) preventive therapy	INH 5 mg/kg/day, max 300 mg/day for nine months	History review	Yes/No	Nominal
Tuberculosis	Active TB.	History review, physical examination, Chest X-Ray, and/or AFB/RMT examination.	Yes/No	Nominal
SLE disease activity²⁵	Based on the SLE disease activity index (SLEDAI-2K) score: 
 • 0 = remission • 1-5 = mild • 6-11 = moderate • ≥ 12 = severe 	History review, physical examination, laboratory examination	As per score	Nominal
Changes in SLE disease activity²⁶	Based on change in SLE disease activity index (SLEDAI-2K) score. Change in score: 
 • increased ≥ 3 = relapse • decreased ≥ 3 = improved • increased but < 3 = active persistent 	History review, physical examination, laboratory examination	As per score	Nominal
Drug-induced hepatotoxicity (INH)	Increase of more than twice the upper limit of normal SGOT/SGPT values and improvement after drug withdrawal ²⁷	History review, physical examination, laboratory examination	Yes/No	Nominal

R value²⁸	Values used to distinguish the type of damage in drug-induced hepatotoxicity. $R = (\text{SGPT value} / \text{upper limit of normal SGPT value}) / (\text{ALP value} / \text{upper limit of ALP value}).$	Laboratory examination	As per the result value	Numerical
Types of damage in drug-induced hepatotoxicity²⁸	Type of damage: 
• Hepatocellular (SGPT ≥ 3 upper limit of normal values and $R \geq 5$).• Cholestatic (ALP ≥ 2 upper limit of normal value and $R \leq 2$).• Mixed (SGPT ≥ 3 upper limit of normal, ALP ≥ 2 upper limit of normal, and $2 < R < 5$).	Laboratory examination	According to the type of damage	Nominal
Severity of drug-induced hepatotoxicity²⁸	
• Grade 0 (No Liver Injury): the patient can tolerate the drugs and there are no signs and symptoms of hepatotoxicity.• Grade 1 (Mild Liver Injury): elevated SGPT and/or ALP values, total bilirubin < 2.5 upper limit of normal (2.5 mg/dL or 42.75 $\mu\text{mol/L}$), INR < 1.5. Most patients show adaptive processes to liver damage. It may be accompanied or without symptoms, such as fatigue, nausea, anorexia, right upper abdominal pain, jaundice, itching, skin redness, or weight loss.• Grade 2 (Moderate Liver Injury): elevated SGPT and/or ALP values,	History review, physical examination, laboratory examination	As per grade	Ordinal

with total bilirubin ≥ 2.5 upper limit of normal or INR ≥ 1.5 . Symptoms and signs of impaired liver function become more apparent.

- *Grade 3 (Severe Liver Injury):* elevated SGPT and/or ALP, total bilirubin ≥ 5 upper limit of normal (5 mg/dL or 85.5 μ mol/L) with or without INR ≥ 1.5 . Symptoms and signs of hepatic impairment are obvious, indicating the need for hospitalisation. There are no signs and symptoms of hepatic encephalopathy.
- *Grade 4 (Acute Liver Failure):* evidence of blood clotting disorders with INR ≥ 1.5 or PTA $<40\%$, signs and symptoms of hepatic encephalopathy, and total bilirubin values ≥ 10 upper limit of normal (10 mg/dL or 171 μ mol/L) or an increase in total bilirubin values ≥ 1.0 mg/dL (17.1 μ mol/L) per day for 26 weeks after the onset of drug-induced hepatotoxicity. Patients may develop ascites and other organ dysfunction.
- *Grade 5 (Lethal):* death caused by drug-induced hepatotoxicity.

Unexpected events²⁹	
 • Grade 1 Mild; asymptomatic or mild symptoms only; clinical observation or diagnosis only; intervention not indicated. • Grade 2 Moderate; minimal, local or non-invasive interventions are indicated; limitation of daily activities based on age. • Grade 3 Severe or medically significant, but not life threatening; indication for hospital admission; limitation of independent daily activities. • Grade 4 Life-threatening; indication for rapid/immediate intervention. • Grade 5 Lethal; associated with an adverse event. 	History review, physical examination, laboratory examination	As per grade	Ordinal
Acid Fast Bacilli (AFB)³⁰	Staining technique to see acid fast bacilli (Mycobacterium tuberculosis) from the sample taken	Laboratory examination	Positive/negative	Nominal
Rapid Molecular Test (RMT)³¹	Rapid PCR (Polymerase Chain Reaction) testing using the GeneXpert platform that can detect TB bacteria	Laboratory examination	Positive/negative	Nominal

Research Duration and Time

This research was conducted from August 2022 to December 2024.

Sample size calculation

The sample size calculation was carried out based on INH prophylaxis studies conducted in HIV patients, obtained the risk of *drug reaction* events of RR 1.2, so that with a confidence level of 95%, power 80%, and effect size 0.5, the sample

size of each group was 27 people, plus 10% to 30 people. Thus, the total number of patients involved is 60 people who will be divided into two groups.

Data Analysis

This study was conducted to assess the safety of INH drug administration in SLE patients by analyzing the increase in SGOT/SGPT values and assessing SLE disease activity measured using SLEDAI. Both will be assessed after two weeks of drug or placebo administration, followed by monthly for the first three months (months 1, 2, 3), then every three months until one year (months 6, 9, 12). Statistical tests used were t-test and/or chi-square by comparing two treatment groups. Results were considered significant when the p value was ≤ 0.05 . Data processing was performed with SPSS version 26 and Stata version 13.

Outputs

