• Liver/Liver Disease:  Ever  Never  Don't Know	SGPT		
• Allergy to INH:  Yes  No  Don't Know	HBsAg		
• Malignancy/Cancer:  Yes  No  Don't Know	Anti HCV		
• Currently on TB treatment:  Yes  No  Don't Know	Creatinine		
• Currently pregnant:  Yes  No  Don't Know		Proteinuria	
Physical Examination		Erythrocytes	
		Leukocytes	
		Cylinders	

*When Clinically Suspicious of TB

Date	Chest X-Ray	AFB	RMT

Active TB: Yes (Clinical/Bacteriological) No

SLEDAI

Parameters	Score	Total	Parameters	Score	Total
Seizures	8		Arthritis	4	
Psychosis	8		Myositis	4	
Organic Brain Syndrome	8		Cylinders	4	
Visual Impairment	8		Haematuria	4	
Cranial Nerve Abnormalities	8		Proteinuria	4	
Lupus Headache	8		Piuria	4	
Cerebrovascular	8		Pleuritis	2	
Vasculitis	8		Pericarditis	2	
New Malar Rash	2		Low complement	2	
Alopecia	2		Anti-dsDNA increased	2	
New/recurrent ulcers	2		Thrombocytopenia	1	
Fever	1		Leukopenia	1	

SLEDAI Total Score: _____ 0 (Remission) 1-5 (Mild) 6-11 (Moderate) ≥ 12 (Severe)

SLE medications: Take SLE medications regularly: Yes No

Medicine	Dosage	Start date	Stop date
 Prednisone/equivalent	mg/day		
 Pulse Steroids	mg/day		
 HCQ/CQ	mg/day		
 Methotrexate	mg/week		
 Azathioprine	mg/day		

 MMF	mg/day	
 Mycophenolic acid	mg/day	
 Leflunomide	mg/day	
 Cyclosporin	mg/N	
 Tacrolimus	mg/day	
 Cyclophosphamide	 NIH  EuroLupus	
 Rituximab		
 More		

CRF INH Safety Study in SLE Patients: Follow Up

Subject Number _____ **No Drug Study** _____
MR Number: Inpatient _____ Rheumatology Clinic _____
Full Name: _____ Gender: F / M _____
Date of Birth (day/month/year): _____ / _____ / _____ Tel/Phone: _____

Visit (____ months from visit __) Date (day/month/year): ___ / ___ / ___

Take medication regularly: Yes No

Clinical	Laboratory	
History review	Hb	

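### The unadjusted comparison leaves unused the background SLE drugs already recorded at Visit 0; adjusting for them is a cheap, modest gain in precision, not the repair of an invalid test

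*Protocol*

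**What the plan says.** Under Research Design and Subjects, allocation is described in one clause: "Subjects who meet the inclusion criteria will be randomly divided into two groups". The text names no stratification, blocking or minimisation factor. The same section keeps lupus treatment going in both arms: "Routine SLE medications will be continued throughout the study and recorded at each visit".

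Entry requires remission or low disease activity, "with a history of stable SLE treatment in the last three months and have good liver function". Previous liver dysfunction is an exclusion; no background drug is.

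The Initial Screening form in Appendix 2 has a block headed "SLE medications: Take SLE medications regularly". It is a checklist with dose, start date and stop date that includes methotrexate, azathioprine and leflunomide. The follow-up SLE medications form repeats the list with doses. SLE medication has no row in the Variables table.

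The liver outcome in that table is: "Increase of more than twice the upper limit of normal SGOT/SGPT values and improvement after drug withdrawal". Data Analysis also compares the SGOT/SGPT values themselves. The method is: "Statistical tests used were t-test and/or chi-square by comparing two treatment groups". The threshold is: "Results were considered significant when the p value was ≤ 0.05".

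**The concern.** The trial asks whether isoniazid is safe for the liver in people already taking several other drugs. Some of those may move the same enzymes, so background treatment is an obvious rival explanation for a liver event. It is collected before allocation, which makes it a legitimate adjustment factor, but the stated analysis makes no use of it.

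In the one trial that is run, a chance surplus of users in the isoniazid arm would push the comparison towards apparent toxicity, and a surplus among controls would push it the other way. The unadjusted analysis also leaves in the error term some variation that could be explained. At stake are the precision of a very small safety comparison and a reader's confidence in attributing individual events.

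**Working it through.** **Inputs from the protocol.** 27 per group, raised by 10% to 30 (27 × 1.1 = 29.7, rounded up to 30); 60 in total; significance at 0.05, sidedness not stated.

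**Inputs assumed.** The protocol gives none of these.
- Share of patients q taking at least one enzyme-raising drug: 30-60%.
- Liver-event risk in users (r1) and non-users (r0): 15-25% v 5%, or a milder 20% v 10%.
- Users' mean log SGPT higher by δ = 0.5-0.8 SD.

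**1. How often do the arms differ in users?** With K users among 60, the number falling in one arm of 30 is hypergeometric.

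| Split | Gap of 6 or more users | Gap of 8 or more users |
|---|---|---|
| 30 + 30 | 16-20% | 5-7% |
| 27 + 27 | 10-17% | 3-5% |

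**2. How much would a gap of 6 move the event count?** The user shares become q + 0.10 and q − 0.10, so the expected difference in events is 30 × 0.20 × (r1 − r0).
- r1 − r0 = 0.10: 30 × 0.20 × 0.10 = 0.6 events.
- r1 − r0 = 0.20: 30 × 0.20 × 0.20 = 1.2 events.

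The standard error of the difference in event counts is √[2 × 30 × p(1 − p)], with p = q·r1 + (1 − q)·r0. At q = 30%, 15% v 5%, p = 0.08 and it is √(60 × 0.0736) = 2.1. At q = 60%, 25% v 5%, p = 0.17 and it is √(60 × 0.1411) = 2.9. A gap of 6 users therefore shifts the result by well under one standard error.

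**3. What remains if users are perfectly balanced?** With equal numbers of users per arm and no isoniazid effect, exact calculation for three scenarios (15% v 5% at 30% users; 25% v 5% at 50%; 20% v 10% at 40%) puts the observed risk ratio at or beyond 1.2 or 1/1.2 in 80-83% of trials. At a 20% event rate the 95% chance range of the risk ratio with 30 per arm is about 0.36-2.75.

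**4. What would adjustment gain?**
- Liver event: R² = q(1 − q)(r1 − r0)² / [p(1 − p)]. At q = 40%, 20% v 10%: 0.24 × 0.01 / (0.14 × 0.86) = 2.0%. At q = 30%, 25% v 5%: 0.21 × 0.04 / (0.11 × 0.89) = 8.6%. Over all the scenarios it is about 2-9%.
- Log SGPT: R² = q(1 − q)δ² / [1 + q(1 − q)δ²]. At q = 30%, δ = 0.5: 0.0525/1.0525 = 5.0%. At q = 50%, δ = 0.8: 0.16/1.16 = 13.8%. As equivalent sample size, 60/(1 − R²) is 63.1 to 69.6, or about 3-10 extra patients.

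**5. Is the test invalid?** No. Over all randomisations the simulated type I error of the unadjusted chi-square was 4.8-5.0%. It departs from 5% only conditionally: given a gap of 6 users, the shift in z for log SGPT is δ × (6/30)/√(2/30), which is 0.39 to 0.62 and gives a two-sided error of 6.7-9.5%. That conditional figure applies only to the minority of allocations in step 1.

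**The case against.** The strongest objection is that nothing here is an error. An unadjusted comparison of randomised groups is valid, and covariates and stratification factors are often left to an SAP, which may exist. The design chart, which might name a stratification factor, was not available either. Validity is fully conceded. What remains is that Data Analysis does name its tests, both are unadjusted, and the data for a better analysis are already on the form.

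Second, a reader might infer that drug imbalance could by itself mimic the risk ratio behind the sample size ("events of RR 1.2, so that with a confidence level of 95%, power 80%, and effect size 0.5"), and so that the result cannot be trusted. The documents do not support this. With 30 per arm, 6 v 5 events is already a ratio of 1.2, and step 3 shows such ratios are routine even with users perfectly balanced. Under the milder contrast (20% v 10%) a gap of 6 users does not reach 1.2. If the drugs raise risk only 1.5-fold, imbalance practically never does. The comparison with 1.2 should be dropped.

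Third, the protocol has partial safeguards. Three months of stable treatment with good liver function selects patients who tolerate their drugs, which may shrink the assumed contrasts. The hepatotoxicity definition also requires improvement after withdrawal. Both stand as mitigation. Neither covers the whole period of continued treatment, and the raw SGOT/SGPT comparison has no attribution step.

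Fourth, pooling three drugs as yes/no is one choice among several, since the form lists others. That is fair, so the list should be the sponsor's, fixed in advance. Finally, the research period ends in December 2024, so changing the randomisation may no longer be possible.

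**Conclusion.** The point holds as an inexpensive improvement. The stated analysis ignores a baseline factor that the trial already records and that plausibly affects its main outcome. The gain is modest: about 2-9% of variance for the liver event and 5-14% for log SGPT, plus a clearer basis for attributing events. It is not a validity problem, and it is smaller than the sampling noise of a trial with 27-30 per arm, which adjustment cannot cure.

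All sizes rest on assumed user shares (30-60%), event risks and enzyme shifts, and on the general-pharmacology premise that these drugs can raise liver enzymes. If few patients take them, or the contrast is weak, the gain falls towards nothing.

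**What to change.** In Data Analysis, prespecify for the liver event a Mantel-Haenszel risk difference with 95% CI, stratified by Visit 0 use (yes/no) of any drug on a named list of enzyme-raising SLE drugs, for example methotrexate, azathioprine and leflunomide. Include the same indicator in the model for SGOT/SGPT.

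Use Visit 0 status only, because later drug changes may be a response to isoniazid or to an enzyme rise. Tabulate baseline use and later changes by arm. If allocation is still open, stratify the randomisation list by the same factor; if it is closed, the change to the analysis stands alone.

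The cost is a sentence or two of text, one extra two-level covariate and, if allocation is open, two lists instead of one. No new data are needed. The drug list must be fixed before outcome data are seen, otherwise the choice of drugs itself becomes a source of bias.

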 Fever  Malaise  Fatigue  Abdominal Pain  Nausea	Ht	
 Vomiting  Icteric	Leukocytes	
 Others:	Platelets	
Physical Examination	Count	Basophils
		Eosinophils
		Neut Rod
		Neut Segment
		Monocytes
		Lymphocytes
	Type	ESR
		SGOT
		SGPT
		Creatinine
	Urinalysis	Proteinuria
		Erythrocytes
		Leukocytes
		Cylinders

SLEDAI Score:

SLEDAI Total Score: 0 (Remission) 1-5 (Mild) 6-11 (Moderate) ≥ 12 (Severe)
SLE Disease Activity: Relapse Improving Persistently Active Remission

Elevated SGOT/SGPT \geq 2x Upper limit of normal values: Yes No

Liver function disorders: Hepatocellular Cholestatic Mixed

Severity: 0 (*No Liver Injury*)

- 1 (*Mild Liver Injury*)
- 2 (*Moderate Liver Injury*)
- 3 (*Severe Liver Injury*)
- 4 (*Acute Liver Failure*)
- 5 (*Lethal*)

Management of Drug-Induced Hepatotoxicity

INH discontinue Continue INH Administration
 Other medications:

Drug-induced hepatotoxicity outcomes

**CRF INH Safety Study in SLE Patients:
SLE recurrence**

Subject Number_____

Full Name: _____ Gender: F / L

Date of Birth (day/month/year): _____ / _____ / _____ Tel/Phone: _____

Visit _____ (months from visit _____) Date (day/month/year): _____ / _____ / _____

SLEDAI score (at time of screening): _____ Remission Mild Moderate Severe

Previous SLEDAI scores: _____

Diagnosis of SLE Recurrence

Clinical (SLE)	
History review	
Physical Examination	

Management of SLE Recurrence (based on rheumatologist's judgement)

- INH discontinue
- Continue INH
- Changes in SLE medications (see CRF for SLE medications, any changes should be noted on the CRF)
- Other medications: _____

SLE Recurrence Outcome

Outputs	SLEDAI Score	Date (day/month/year)
 Relapse		
 Improving		
 Active Persistent		
 Remission		
 Died		
 Others:		

CRF INH Safety Study in SLE Patients:
SLE medications

No Subject _____

Full Name: _____ Gender: F / M

Date of Birth (day/month/year): _____ / _____ / _____ Tel/Phone: _____

Visit (____ months from visit ____) Date (day/month/year): ____ / ____ / ____

Take SLE medication regularly: Yes No

SLE medications

Medicine	Dosage
 Prednisone or equivalent	mg/day
 Pulse Steroids	mg/day

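### Does the SLE relapse definition need amending because it names no reference score and leaves some score changes without a class?

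*Protocol*

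**What the plan says.** The Aim names two safety questions, liver toxicity and disease recurrence. In the Variables table, the row on changes in SLE disease activity gives the rule for the second, using the SLEDAI-2K: "increased ≥ 3 = relapse • decreased ≥ 3 = improved • increased but < 3 = active persistent". The row above it defines levels of activity, beginning "0 = remission • 1-5 = mild". No reference visit is stated for the change.

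Appendix 2 holds the case report forms.

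- The Initial Screening form lists the item weights and records a "SLEDAI Total Score".
- The Follow Up form records the total again and offers four boxes: "SLE Disease Activity: Relapse Improving Persistently Active Remission".
- The SLE recurrence form has a field beginning "SLEDAI score (at time of screening" with four activity levels to tick, then a field "Previous SLEDAI scores", and later a table headed "SLE Recurrence Outcome".

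Data Analysis says that SLE disease activity is assessed with the SLEDAI and that the groups are compared by t-test and/or chi-square. It names no relapse proportion as the tested outcome.

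**The concern.** A change score needs a starting point, and here two are available. The recurrence form appears to carry both a screening score and earlier scores without saying which decides. There are seven follow-up visits (months 1/2, 1, 2, 3, 6, 9 and 12). The two references must coincide only at the first, so they can part at the other six. Two assessors who both follow the text could label the same patient differently, and an analyst could choose the reference after seeing the data.

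The classes also look incomplete. Patients enter in remission or low disease activity on stable treatment, so an unchanged score or a small fall is a plausible result at many visits, yet neither has a class. The Follow Up form adds remission, which is a level and not a change, and so overlaps improvement. If relapse were compared by chi-square in a trial of 60 patients, a few reclassified patients could matter.

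**Working it through.** The protocol states no relapse rate or count, so there is no figure to reproduce. The check is whether the two readings differ, and what the missing classes affect.

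**Can the readings differ?** Inputs: the cut-off of +3 (Variables) and the item weights on the Initial Screening form, namely alopecia 2, "New/recurrent ulcers" 2 and arthritis 4.

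| Scores | Change from screening | Change from previous visit | Relapse against |
|---|---|---|---|
| 0, 2, 4 | +2, +4 | +2, +2 | screening only |
| 4, 2, 0, 4 | -2, -4, 0 | -2, -2, +4 | previous visit only |

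Both paths can be built from the form's own weights: none, alopecia, alopecia plus ulcers; and alopecia plus ulcers, alopecia, none, arthritis. So the readings differ, and in both directions.

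**How often?** One can count all paths of an entry score s from 0 to 5 and two follow-up scores f1 and f2. The highest follow-up score allowed is an assumption.

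*Follow-up scores 0 to 12* (6 × 13 × 13 = 1,014 paths):

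- Relapse only against screening needs two rises, each at most 2, summing to at least 3: (1,2), (2,1) or (2,2). That is 3 × 6 entry scores = 18.
- Relapse only against the previous visit needs f2 ≤ s + 2 and f1 ≤ f2 - 3. For s = 0 to 5 this gives 0 + 1 + 3 + 6 + 10 + 15 = 35.
- No relapse against screening: the sum of (s + 3)² = 9 + 16 + 25 + 36 + 49 + 64 = 199. Neither reading: 199 - 35 = 164.
- Both readings: 1,014 - 164 - 18 - 35 = 797.
- Disagreement: 18 + 35 = 53 of the 850 paths with a relapse under at least one reading, or 6.2%.

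*Follow-up scores 0 to 5* (6³ = 216 paths): 50 under both, 8 only against screening, 22 only against the previous visit, 136 under neither. Disagreement: 30 of 80, or 37.5%.

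The share moves sixfold with the cap alone (37.5 / 6.2 = 6.0). A cap of 5 also bars every patient from the protocol's moderate (6 to 11) and severe (12 or more) levels. These counts give every path equal weight, so they are not patient frequencies. They show that the readings can differ and say nothing on how often they will.

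**What do the missing classes touch?** Of the 36 pairs of entry and follow-up scores within 0 to 5:

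- rise of 3 or more: 6
- rise of 1 or 2: 5 + 4 = 9
- change of 0, -1 or -2: 6 + 5 + 4 = 15, with no class in Variables
- fall of 3 or more: 6

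Of the 15, three end at 0 (0 to 0, 1 to 0, 2 to 0) and fit the remission box on the Follow Up form, which leaves 12. Three others (3, 4 or 5 to 0) fit both improvement and remission. None of these pairs is a rise of 3 or more, so the relapse count is the same however they are labelled. A t-test on SLEDAI scores does not use the classes.

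**Does the recurrence form decide?** It leans one way without settling the matter. Its first SLEDAI field offers moderate and severe as options. These would serve little purpose for a visit-0 score, since patients must enter in remission or low activity. The field may therefore mean the score at the current examination, set beside the previous ones. Against that, the wording says screening, the second field is plural, and the Variables table is silent.

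**The case for a change.** The strongest case for acting is that the protocol did not leave this outcome open. It chose the instrument, the threshold and the classes, and wrote a rule that cannot be applied without one more fact. Recurrence is half of the aim. The forms are completed by assessors who know the allocation, so an unnamed reference permits inconsistent ticking and a late choice. Naming it would cost one sentence.

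Part of this stands. The reference is missing, the two readings are not equivalent, and the four follow-up boxes are neither exhaustive nor mutually exclusive. An analyst should state the reference used and derive relapse from the recorded totals, not from the ticked box.

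The rest is weaker. Because the totals are recorded at visit 0 and at follow-up, an inconsistent tick does not lose the outcome. Open-label knowledge could affect how the SLEDAI items are scored, but naming a reference would not cure that. Choosing the reference visit for a derived change is routine work for a statistical analysis plan, which may exist but was not available here. Preferring visit 0 would itself be a matter of taste: a flare after improvement (4, 2, 0, 4) would then drop out of the main count, whereas the previous visit misses the slow rise (0, 2, 4).

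**Conclusion.** No change to the plan is called for. The omission is a missing detail that a competent analyst fills from data already collected. Relapse is fixed as a rise of at least 3 points on the SLEDAI-2K, both candidate references are sound, and either can be computed, with the other as a check. The gap at 0, -1 and -2 and the overlap of remission with improvement are matters of labelling that leave the relapse count and a comparison of mean scores untouched.

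The possible effect is 1/30 = 3.3 percentage points in an arm's relapse rate for each patient whose status depends on the reference. How many such patients there would be, and whether any p-value would move, cannot be estimated from the protocol. The conclusion assumes that SLEDAI totals are completed at visit 0 and at each follow-up visit, as the forms provide, and that the reference is chosen without regard to the results by arm.

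### The only Yes/No liver event in the Variables table requires improvement after drug withdrawal, so controls cannot meet it and it cannot serve as the between-arm liver outcome

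*Protocol*

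**What the plan says.** The Variables table of the protocol has a row for INH hepatotoxicity with a Yes/No output, defined as "Increase of more than twice the upper limit of normal SGOT/SGPT values and improvement after drug withdrawal". The other liver rows are a numerical R value, a damage type and an ordinal severity grade, so this is the only Yes/No liver event in the table.

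Research Design describes the groups as "those receiving INH and pyridoxine for nine months and those not receiving both drugs". Research Design and Subjects repeats this ("and the control group receiving neither drug") and adds: "Routine SLE medications will be continued throughout the study and recorded at each visit".

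Three other places bear on how the row would be used:

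- Research Design states that "Signs and symptoms of drug-induced hepatotoxicity and degree of SLE disease activity were assessed monthly for the first three months", then at months 6, 9 and 12.
- Data Analysis says safety will be judged "by analyzing the increase in SGOT/SGPT values and assessing SLE disease activity measured using SLEDAI", with a t-test and/or chi-square between the two groups and significance at p ≤ 0.05.
- The follow-up CRF in Appendix 2 has a separate tick item for raised SGOT/SGPT, ending "2x Upper limit of normal values: Yes No", with no withdrawal condition.

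The severity row defines Grade 5 as "death caused by drug-induced hepatotoxicity". The follow-up CRF's block on managing drug-induced hepatotoxicity offers both stopping and continuing INH.

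**The concern.** The aim is to show that INH is safe for the liver, by comparison with untreated controls. An outcome for that comparison must be attainable in both arms by the same rule. This row fails in two ways.

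In controls there is no INH to withdraw, so the second half of the definition cannot be met. If drug were read as any drug, a control could qualify only after an SLE medicine was stopped. The protocol says those continue, although the SLE recurrence CRF allows changes.

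In the INH arm, only rises that are followed by withdrawal and then improve are counted. Persistent rises drop out of the rate.

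The bias can therefore run in either direction. Background rises that settle after stopping count against INH, with nothing to offset them in controls. Rises that do not settle are not counted at all, which works against a trial meant to establish safety.

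**Working it through.** **1. The definition set against the rest of the protocol**

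| Situation | Scored by the Variables row | Treated elsewhere as |
|---|---|---|
| Control, enzymes above the threshold | No (no INH to withdraw) | Yes on the follow-up CRF tick item |
| INH arm, rise persists after stopping | No | Drug-induced hepatotoxicity on the severity scale |
| INH arm, INH continued | No, as the withdrawal condition is not yet met | Managed under the CRF's drug-induced hepatotoxicity block |
| INH arm, liver death | No (no improvement) | Grade 5 drug-induced hepatotoxicity |
| INH arm, rise improves after the planned end at month 9 | Not stated | Only the month 12 visit follows |

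The threshold differs too: strictly above twice the upper limit of normal in the table, at or above twice on the CRF.

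**2. Inputs for the size of the effect**

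- From the protocol: 30 per arm (27 plus 10%, taken as given), p ≤ 0.05, chi-square.
- Assumed, because the protocol gives no event rates: background risk *q* of an enzyme rise (5%, 10%, 20%), and *w*, the share of INH-arm rises that are withdrawn and improve (0.25 to 1). Each participant has one event status.
- Under the row, the control event probability is 0 and the INH-arm probability is *q* × *w*.

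**3. Events needed for significance against 0/30**

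For *a*/30 v 0/30:

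- Uncorrected chi-square = 60*a*/(60 − *a*). *a* = 3: 180/57 = 3.16, p = 0.076. *a* = 4: 240/56 = 4.29, p = 0.038. Four events are needed.
- Yates = 60(*a* − 1)²/[*a*(60 − *a*)]. *a* = 5: 960/275 = 3.49, p = 0.062. *a* = 6: 1500/324 = 4.63, p = 0.031. Six are needed.
- Fisher: *a* = 5, p = 0.052; *a* = 6, p = 0.024. Six are needed.

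**4. False significance with no INH effect**

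The rate is P(X ≥ 4), or P(X ≥ 6) for Fisher and Yates, with X ~ Binomial(30, *qw*). For *q* = 0.10 and *w* = 1, P(X ≥ 4) = 0.353. The arm-neutral column sums over both arms with probability *q* in each.

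| Test | *q* | *w* = 0.25 | 0.5 | 0.75 | 1 | Arm-neutral item |
|---|---|---|---|---|---|---|
| Uncorrected | 5% | 0.05% | 0.6% | 2.5% | 6.1% | 2.8% |
| Uncorrected | 10% | 0.6% | 6.1% | 18% | 35% | 5.4% |
| Uncorrected | 20% | 6.1% | 35% | 68% | 88% | 4.9% |
| Fisher/Yates | 5% | 0.00% | 0.01% | 0.08% | 0.3% | 0.15% |
| Fisher/Yates | 10% | 0.01% | 0.3% | 2.2% | 7.3% | 0.9% |
| Fisher/Yates | 20% | 0.3% | 7.3% | 29% | 57% | 2.2% |

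With 27 per arm and *q* = 10%, the uncorrected figures are 0.4%, 4%, 14% and 28% (arm-neutral 5.2%).

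**5. The opposite direction**

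Take true risks of 30% (INH) v 10% (control) and *w* = 0.25. The arm-neutral difference is 0.30 − 0.10 = 0.20. Under the row it is 0.30 × 0.25 − 0 = 0.075. Power falls from 50% to 18% uncorrected, and from 37% to 2% with Fisher. The two biases cancel in the difference only when 0.30*w* = 0.20, that is *w* = 0.67.

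**The case against.** The protocol never says that this row is the between-arm outcome. It sits in a table of definitions beside age and disease duration. Data Analysis speaks of increases in enzyme values, for which a t-test is natural, and carries no withdrawal clause. Research Design refers to signs and symptoms of hepatotoxicity, which can be recorded in controls. The follow-up CRF already places an arm-neutral tick item apart from the hepatotoxicity management block. The cases that the row excludes are still captured by the severity and unexpected-events rows and the laboratory values. The large error rates need assumed background risks in patients selected for good liver function. They also need the uncorrected chi-square, although at 10% background with every rise qualifying the expected event count per arm is only (3 + 0)/2 = 1.5.

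Most of this stands, and it limits the concern: the harm is conditional, the data are recoverable and the size depends on assumptions. It does not remove the concern. A chi-square test needs a categorical variable, Data Analysis names none for the liver, and the only Yes/No liver variable that the protocol defines is this one. The CRF item is not in the Variables table, uses a different threshold sign, and is nowhere stated to be the measure compared. An analyst following the protocol could choose either. Nor is this detail left to an analysis plan: the definition that is written down is unsuitable for a between-arm comparison.

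**Conclusion.** The concern holds and should be fixed. On its natural reading, the row gives a control rate of zero by construction and an INH rate restricted to cases that were withdrawn and improved. It also conflicts with the protocol's own use of the term in Grade 5 and in the CRF management block. That conclusion depends on no assumed rate.

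The numerical consequence applies only if the row is compared between arms, and it rests on assumed values of background risk and *w*. It runs from negligible (5% background, most values of *w*) to large (10% background or more with most rises qualifying, especially with the uncorrected test). It can also turn into a serious loss of power to detect real harm when few rises qualify. If the CRF item is compared, the problem does not arise.

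**What to change.** Split the row in two.

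1. **Between-arm outcome:** SGOT or SGPT elevation relative to twice the upper limit of normal at a post-baseline visit, judged identically in both arms regardless of withdrawal or recovery. Use the existing follow-up CRF item, with one threshold sign in the table and on the CRF.
2. **Causality descriptor, INH arm only:** improvement after withdrawal, reported descriptively, with a statement on whether improvement after the planned end of INH counts.

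Reconcile the causality row with Grade 5 and with the CRF management block, so that the term has one meaning throughout. As a minor wording point, the mention of placebo in Data Analysis should be reconciled with the untreated control described in Research Design.

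The cost is a rewording of one table row and the alignment of one sign. SGOT, SGPT and the Yes/No item are already on the follow-up CRF, so no new data are needed and no rule on treatment changes.
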